17.5 Additional analyses

An additional evaluation of the primary endpoint will be made, including actual concizumab dose level as *additional factor in the primary analysis model specified above*. Point estimates and 95% confidence interval will be provided for the ABR at the different dose levels of concizumab (0.15, 0.20 and 0.25 mg/kg). Furthermore, an analysis with individual steady state PK/PD assessments included as covariates in the negative *binomial regression model as specified for the primary analysis* will be performed in order to evaluate possible associations between PK/PD and ABR that potentially could guide dose-selection. The referred steady-state PK/PD assessments comprise the concizumab trough level, maximum plasma concentration (C_{max}) of concizumab, TFPI value prior to the last s.c. dose administration, peak thrombin generation (nM), Endogenous thrombin potential (nM*min) and velocity index (nM/min).

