17.6.4 Supportive secondary pharmacodynamic endpoints

Free TFPI concentration:

- Value prior to the last dose administration at 24 weeks.
- Value prior to the last dose administration at 76 weeks.

Thrombin generation:

- Peak thrombin generation (nM) prior to the last dose administration at 24 weeks.
- Peak thrombin generation (nM) prior to the last dose administration at 76 weeks.
- Endogenous thrombin potential (nM*min) prior to the last dose administration at 24 weeks.
- Endogenous thrombin potential (nM*min) prior to the last dose administration at 76 weeks.
- Velocity index (nM/min) prior to the last dose administration at 24 weeks.
- Velocity index (nM/min) prior to the last dose administration at 76 weeks.

The PD endpoints will be summarized and listed.

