Turoctocog alfa (rFVIII) 2000 IU/vial and isotonic sodium chloride (solvent). Turoctocog alfa (rFVIII) is for intravenous administration.

Table 2-2 Flow chart explanatory descriptions

Footer	Description
a	Concizumab administration is performed at home except for visit 2 where concizumab administration will take place at the trial site.
b	The duration of the visits will last according to patient's individual training need on concizumab administration, NovoPen [®] 4, eDiary training etc. Visit 3 will be a phone call to the patient.
c	For patients being dose escalated a phone call is recommended 1 week after first new dose of concizumab.
d	Daily dosing preferably at the same time in the morning.
e	Evaluation of laboratory results obtained from samples taken at screening.
f	Bleeding episodes occurring between visit 1 and visit 2 or at site should be registered in the eCRF. All bleeding episodes except for severe occurring after visit 2 at home should be registered in the eDiary. Severe bleeding episodes must be registered in the eCRF.
g	Turoctocog alfa will be given to treat breakthrough bleeding episodes either in the clinic or at home.
h	At visit 9 and 16 all blood samples should be collected pre-dose. Patients must not treat themselves with concizumab until sampling has been performed. For unscheduled PK-session visit; patients must not treat themselves with concizumab until pre-dose sampling for thrombin generation, concizumab ELISA and Free TFPI has been collected.
i	Only body weight should be measured.
j	Vital signs should be evaluated before and after trial drug administration at visit 2.
k	Sampling for FVIII activity at screening should be postponed if the patient has received FVIII within 96 hours and medical records documenting the severity of haemophilia are not available.
l	FVIII activity and FVIII inhibitor tests should only be collected if reduced effect of turoctocog alfa or FVIII inhibitor development is suspected.
m	In case of clinical signs of e.g. hypersensitivity reactions or immune related events are seen, additional samples for ADAs may be taken. All antibody samples from the affected patient will be analysed on an ongoing basis. If antibodies are detected additional samples will be taken and stored for characterisation of the antibodies.
n	Only dispensing of turoctocog alfa and sodium chloride.

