4.2.2 Secondary endpoints

4.2.2.1 Supportive secondary endpoints

- **Supportive secondary efficacy endpoints**
- The number of bleeding episodes during 76 weeks from treatment onset
- The number of spontaneous bleeding episodes during at least 24 weeks from treatment onset
- The number of spontaneous bleeding episodes during 76 weeks from treatment onset
- **Supportive secondary safety endpoints**
- Number of treatment-emergent adverse events (TEAEs) during at least 24 weeks from treatment onset
- Number of TEAEs during 76 weeks from treatment onset
- Occurrence of anti-concizumab antibodies during at least 24 weeks from treatment onset
- Occurrence of anti-concizumab antibodies during 76 weeks from treatment onset
-
- Change from baseline of fibrinogen during 24 weeks from treatment onset
- Change from baseline of fibrinogen during 76 weeks from treatment onset
- Change from baseline of D-dimer during 24 weeks from treatment onset
- Change from baseline of D-dimer during 76 weeks from treatment onset

Protocol
 Trial ID: NN7415-4255
 UTN: U1111-1179-3872
 EudraCT no.: 2016-000614-29

~~CONFIDENTIAL~~

Date: 28 December 2017
 Version: 4.0
 Status: Final
 Page: 27 of 124

Novo Nordisk

- Change from baseline of prothrombin fragment 1 + 2 (F1 + 2) during 24 weeks from treatment onset
- Change from baseline of F1 + 2 during 76 weeks from treatment onset
- Change from baseline of prothrombin time (PT) during 24 weeks from treatment onset
- Change from baseline of PT during 76 weeks from treatment onset
- Change from baseline of activated partial thromboplastin time (APTT) during 24 weeks from treatment onset
- Change from baseline of APTT during 76 weeks from treatment onset
- Change from baseline of antithrombin (AT) during 24 weeks from treatment onset
- Change from baseline of AT 76 weeks from treatment onset
-

Supportive secondary pharmacokinetic endpoints

- Concentration of concizumab prior to the last dose administration at 24 weeks
- Concentration of concizumab prior to the last dose administration at 76 weeks

Supportive secondary pharmacodynamic endpoints

Plasma free TFPI concentration

- Value prior to the last dose administration at 24 weeks
- Value prior to the last dose administration at 76 weeks

Thrombin generation

- Peak thrombin generation (nM) prior to the last dose administration at 24 weeks
- Peak thrombin generation (nM) prior to the last dose administration at 76 weeks

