8.1.7 Visit 1 (Screening part)

Informed consent must be obtained before any trial related activity, see Section [18.2](#).

In cases where a patient's baseline FVIII level is not documented in medical records, sampling for FVIII activity at screening should be postponed if the patient has received FVIII within 96 hours. Screening can take place between 14 to 21 days prior to planned enrolment day (visit 2). For prophylactic treatment (prior to Screening) with extended half-life FVIII products, this period should be extended to a time-period equal to 8 half-lives of the used product

All assessments to be performed at screening are listed in [Table 2-1](#), see Section [2](#).

Apart from informed consent patients will be asked to complete the ePRO questionnaires before any other trial related activities are performed according to Section [8.6](#);

- Hemo-TEM,
- VERITAS-Pro[®] or VERITAS-PRN[®]

Assessment results from physical examination, body measurements, as well as measurements of vital signs, urinalysis electrocardiogram (ECG) and details of any contemporary adverse events must be entered into the eCRF.

A screening confirmation call must be performed in the IWRS, at the day of the visit.

The investigator must review all information obtained from the screening procedures. If a patient does not meet all inclusion criteria or meets one or more of the exclusion criteria for the trial the patient does not qualify to be enrolled.

Patients will be provided with turoctocog alfa (rFVIII) trial injection kits and directions for use (DFU) to cover the potential FVIII treatment in the screening part of the trial and investigator will ensure that the patients are capable of treating themselves with rFVIII (turoctocog alfa). Patients on any previous FVIII prophylaxis can continue with this treatment until 48 hours before visit 2.

Dispensing of rFVIII (turoctocog alfa) should be performed in the IWRS

For bleeding episodes that occur in the period from Screening visit (Visit1) to enrolment visit (Visit 2) information about the bleeding episode is to be entered in the eCRF at visit 2.

Protocol
 Trial ID:NN7415-4255
 UTN:U1111-1179-3872
 EudraCT no.:2016-000614-29

~~CONFIDENTIAL~~

Date:	28 December 2017	Novo Nordisk
Version:	4.0	
Status:	Final	
Page:	45 of 124	

The patient should be instructed to call the site if any bleeding episodes, questions or issues arise after he has left the site.

8.1.8 Training of patients visit 1 and visit 2

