8.1.9 Treatment period - Main part

8.1.9.1 Visit 2 (Assessment, 1st concizumab treatment at site)

Visit 2 should be scheduled 14 to 21 days after visit 1. The date of visit 2 will be considered as trial day 1.

Before any concizumab administration it is important to verify the in/exclusion criteria again and review central laboratory test results from screening.

The patient must be in a non-bleeding state at the time of first administration with concizumab and should not have received any FVIII treatment for prophylaxis or for treatment of a bleeding episode within a period of 48 hours prior to dosing.

Patients will be asked to complete the ePRO questionnaires before any other trial related activities are performed according to section [8.6.1](#);

- Hemo-TEM,
- SF-36v2,
- SDS,
- TSQM,
- SIAQ-ISRQ

All protocol assessments must be performed before 1st administration of concizumab. Vital signs must be assessed both before and after concizumab administration.

Assessment results from concomitant medication, vital signs, Body measurements (weight only) and details of adverse events must be entered into the eCRF.

Protocol
 Trial ID:NN7415-4255
 UTN:U1111-1179-3872
 EudraCT no.:2016-000614-29

~~CONFIDENTIAL~~

Date:	28 December 2017	Novo Nordisk
Version:	4.0	
Status:	Final	
Page:	46 of 124	

At this, the 1st treatment visit, the allocated dose of concizumab will be given. Concizumab will be administered at the trial site supervised by medically trained trial staff.

The time point at which the completion of the first dose takes place corresponds to Time on treatment = 0 and must be recorded in the eCRF.

The patient must be observed at the trial site for at least 2 hours after the administration of the first dose of concizumab.

In order to determine the correct amount of the patient's daily dose of concizumab, until next scheduled visit, investigator will consult the dosing-table in the TMM on basis of the patient's current body weight.

Investigator will communicate any the daily dose of concizumab to the patient and record the dose for the coming home treatment period in the eCRF.

Prior to the first dose a dispensing call must be performed in the IWRS.

At the visit the patient will be provided with trial product (concizumab and if necessary rFVIII (turoctocog alfa)) and injection kits as well as an eDiary device to be able to conduct and report home treatment until the next scheduled visit.

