8.1.9.5 Visit 9 (Assessment visits)

Visit 9 is to be scheduled on trial day 169 (24 weeks) with a visit window of ± 7 days.

Treatment with concizumab must take place after the blood sampling at this visit.

Patients will be asked to complete the PRO questionnaires before any other trial related activities are performed according to section [8.6.1](#);

- PGI-C
- Hemo-TEM
- SF-36v2
- SDS
- TSQM
- H-DAT
- SIAQ-ISRQ

Assessments are to be performed according to [Table 2–1](#) and the assessment results from physical examination, concomitant medication, vital signs, Body measurements (weight only) and details of adverse events must be entered into the eCRF.

Investigator is to perform compliance check of treatment and reporting of bleeding episodes through the available access to collected data from the eDiary. Based on the assessment of any spontaneous bleeding episodes the investigator must evaluate if an escalation of the concizumab doses is needed according the escalation rules described in section [5.3.1](#). All decisions to escalate the concizumab dose must be recorded in the eCRF.

The patient will be asked to return all used, partly used and unused concizumab cartridges and turoctocog alfa (FVIII) during the trial as instructed by the investigator. Drug accountability must be performed at all visits for concizumab and rFVIII (turoctocog alfa) including injection kits, if applicable. Unused sodium chloride syringes should be returned to site at every visit and new sodium chloride syringes should be dispensed to the patient.

In order to determine the correct amount of the patient's daily dose of concizumab, until next scheduled visit, investigator will consult the dosing-table in the TMM on basis of the patient's current body weight. Investigator will communicate any corrections in the daily dose of concizumab to the patient and record the dose for the coming home treatment period in the eCRF.

A dispensing call must be performed in the IWRS.

Protocol
Trial ID:NN7415-4255
UTN:U1111-1179-3872
EudraCT no.:2016-000614-29

~~CONFIDENTIAL~~

Date:	28 December 2017	Novo Nordisk
Version:	4.0	
Status:	Final	
Page:	49 of 124	

At the visit the patient will be provided with trial product (concizumab and if necessary rFVIII (turoctocog alfa)) and injection kits to be able to conduct home treatment until next scheduled visit.

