8.5.2.6 FVIII inhibitor test

The inhibitor level of the patient will be measured by the Nijmegen method at visit 1 (screening).

- FVIII inhibitor titre (BU)

In order to minimise the risk of false negative results, circulating FVIII product levels should be less than 0.05 IU/ml, when sampling for the test. If the patient has received FVIII within 96 hours of screening, the sampling of FVIII-Inhibitor should be postponed until a time period equal to 8 half-lives of the used product has passed (counting from latest treatment).

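### Thrombin generation and APTT samples are not protected from recent FVIII, which ties change in APTT to prior regimen and works against the section 17.5 association with ABR

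*Protocol*

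**What the plan says.** Section 8.1.9.1 asks that before first dosing at visit 2 the patient should not have had "any FVIII treatment for prophylaxis or for treatment of a bleeding episode within a period of 48 hours prior to dosing". Section 8.1.7 lets prophylaxis run to that limit: "Patients on any previous FVIII prophylaxis can continue with this treatment until 48 hours before visit 2".

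For weeks 24 and 76 the only timing rule concerns concizumab. Table 2-2, note h, says "At visit 9 and 16 all blood samples should be collected pre-dose", and section 8.1.9.5 says "Treatment with concizumab must take place after the blood sampling at this visit"; section 8.1.10.3 does the same for visit 16. No FVIII-free interval is given, although section 5.3.2 allows FVIII for breakthrough bleeds throughout.

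Other assays are treated differently. Section 8.5.2.6 wants circulating FVIII below 0.05 IU/mL for the inhibitor test and, if FVIII was given within 96 h, says that sampling "should be postponed until a time period equal to 8 half-lives of the used product has passed". Section 8.1.7 postpones the FVIII activity sample if FVIII was given within 96 h and the baseline level is undocumented.

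On analysis, one APTT endpoint is "Change from baseline of activated partial thromboplastin time (APTT) during 24 weeks from treatment onset", with a 76-week counterpart. The thrombin generation endpoints (peak, ETP, velocity index) are absolute pre-dose values at weeks 24 and 76, of which section 17.6.4 says "The PD endpoints will be summarized and listed". Section 17.5 adds "an analysis with individual steady state PK/PD assessments included as covariates" in the bleeding-rate model, naming the three thrombin generation measures and noting that the associations could guide dose selection.

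**The concern.** Section 3.1.1 itself explains that without FVIII the thrombin burst is delayed and too weak, so infused FVIII raises thrombin generation whether or not concizumab works. That FVIII deficiency prolongs APTT and replacement shortens it is standard laboratory knowledge, taken as given here.

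Two results are exposed. First, prophylaxis and on-demand patients are both eligible. Those from prophylaxis may reach visit 2 with residual FVIII, while most on-demand patients will not. If visit 2 is baseline, the change in APTT then mixes the effect of concizumab with loss of earlier FVIII, to a degree that depends on prior regimen.

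Second, after visit 2 the FVIII comes mainly from bleed treatment. The more a patient bleeds, the likelier a sample falls soon after an infusion. In section 17.5 that places raised thrombin generation in patients with high ABR, opposite to the pattern expected if thrombin generation protects against bleeding. That analysis is one the sponsor may use for phase 3 dose guidance.

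**Working it through.** The plan states no figure to reproduce here. The inputs are:

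- Recovery: 2 IU/dL per IU/kg (section 8.3.1).
- Single-dose cap for bleeds: 50 IU/kg (section 5.3.2). The protocol gives no prophylaxis dose; 25 IU/kg is assumed as a lower value.
- FVIII half-life: not stated. Assumed 8-14 h for non-modified products. A value of 12 h follows only if 96 h and 8 half-lives describe the same period (96 / 8 = 12).
- Design ABR 4, 24-week over-dispersion 6, six months on average (section 17.1); threshold ABR 12.

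**Residual FVIII before visit 2.** Residual = dose × 2 × 0.5^(t / half-life), ignoring accumulation and endogenous FVIII. In IU/dL:

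| Dose | t | 8 h | 12 h | 14 h |
|---|---|---|---|---|
| 25 IU/kg | 48 h | 0.8 | 3.1 | 4.6 |
| 50 IU/kg | 48 h | 1.6 | 6.3 | 9.3 |
| 25 IU/kg | 96 h | 0.01 | 0.20 | 0.43 |
| 50 IU/kg | 96 h | 0.02 | 0.39 | 0.86 |

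For example, 50 × 2 × 0.5^(48/12) = 6.25. At 48 h all but the lowest value exceed the 1% that defines severe disease. The protocol's inhibitor-test limit (0.05 IU/mL = 5 IU/dL) is exceeded only after 50 IU/kg at 12 h or longer. At 96 h every value is below 1 IU/dL.

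**Share of visit 9 samples after rescue FVIII.** With bleeds as a Poisson process, P = 1 − exp(−ABR × window / 365.25). The window is 4 days if only a bleed starting in the last 96 h counts, and 5-8 days if 1-4 treatment days per bleed (assumed) are added.

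- ABR 4: 4.3% at 4 days; 1 − exp(−4 × 5 / 365.25) = 5.3%; 8.4% at 8 days. Of 30 patients, about 1.3 to 2.5.
- ABR 12: 12.3% at 4 days, 15.1% at 5 days, 23.1% at 8 days. Of 30 patients, about 3.7 to 6.9.

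A negative binomial check at ABR 4 and 4 days, with k = (6 − 1) / (4 × 0.5) = 2.5 and mean 4 × 4 / 365.25 = 0.0438, gives 1 − (1 + 2.5 × 0.0438)^(−1/2.5) = 4.1%. Over-dispersion hardly changes the average; it concentrates affected samples in frequent bleeders.

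**What is recorded.** Section 8.3.1 collects dose, date and time of FVIII given for bleeds. For prophylaxis, section 8.2.4 collects dosage and frequency in the year before screening, and section 8.2.3 collects start and stop dates of concomitant medication. Neither asks for the time of the last infusion before visit 2.

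**The case against.** The strongest reply is that excluding or flagging PD samples, and defining baseline, is ordinary SAP work, and the SAP is not shown. This stands for the analysis rule. It does not cover the sampling condition or the recording of the last prophylactic infusion; an SAP cannot recover a time that was never collected.

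Second, the stricter intervals were written for other purposes: documenting severity and avoiding false-negative inhibitor results. They are not stated limits for APTT or thrombin generation. This stands; they are used here only as a flagging interval the protocol already contains.

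Third, the section 17 text available is version 3. The version 4.0 text available stops before section 17, and a laboratory manual may add sampling rules. This stands as a caveat.

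Fourth, excluding samples outright would remove prior-prophylaxis patients at baseline and poor responders later. This stands and shapes the fix.

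A reader might also infer that the 48 h rule distorts the thrombin generation endpoints. It does not, because they are not changes from baseline. Nor do the documents support a general reading that these endpoints measure FVIII rather than concizumab: at the design ABR more than nine in ten visit 9 samples are clear. Residuals for extended half-life products are not a sound headline figure either, since section 5.3.3 prohibits those products in the trial and section 8.1.7 has a separate, loosely worded provision for prior users.

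**Conclusion.** The concern holds for two secondary results. Change in APTT can carry prior regimen into the baseline, with about 0.8-9.3 IU/dL of FVIII left at 48 h; this requires that visit 2 is baseline, which the text available does not say, and rests on the assumed doses and half-lives. The section 17.5 association is exposed to outcome-dependent contamination in about 4-8% of visit 9 samples at ABR 4 and 12-23% at ABR 12. Its direction is clear, against the expected association, but the size of the resulting bias was not computed. Section 17.5 also does not tie the steady-state value to visit 9, so that share is a guide.

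The absolute week 24 and 76 thrombin generation values are affected only in this minority, and the primary bleed count not at all. The issue should be corrected but does not threaten the trial's main conclusion.

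**What to change.** - Record the date and time of the last FVIII infusion, including prophylaxis before visit 2, at each thrombin generation and APTT sample.
- Flag samples taken within the interval the protocol already uses (96 h / 8 half-lives).
- In section 17.5, use the nearest unflagged steady-state sample. Section 8.5.1.1 samples thrombin generation at every visit except visit 3, so alternatives should usually exist.
- Report section 17.6.2 (APTT) and section 17.6.4 with and without flagged samples. State which visit is the APTT baseline; use an unflagged visit 1 or visit 2 value where one exists, and otherwise show the change by prior regimen.
- Reconcile sections 8.1.7, 8.1.9.1, 8.1.9.5, 8.1.10.3 and 8.5.2.6 on what they require about FVIII before coagulation sampling.

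No change to FVIII treatment is proposed. The cost is one added data item plus protocol and SAP wording. The downside is fewer unflagged values in prior-prophylaxis patients at baseline and in frequent bleeders later, which is why flagging with a paired report is preferable to outright exclusion.

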8.1.9.2 Treatment period at home

Home treatment is defined as self-administration of trial product, performed independently by the patient, preferably in the morning. Home treatment starts after visit 2 or when the patient is comfortable self-administering trial product subcutaneously (concizumab) and intravenously (turoctocog alfa (FVIII)).

8.1.9.3 Visit 3 (Phone visit)

Visit 3 is to be scheduled as a phone contact (or similar) 7 days after visit 2 (with a visit window of +1 day).

All relevant protocol assessments listed in [table 2-1](#) must be discussed. Assessment results from concomitant medication and details of adverse events must be entered into the eCRF.

Protocol
Trial ID:NN7415-4255
UTN:U1111-1179-3872
EudraCT no.:2016-000614-29

~~CONFIDENTIAL~~

Date:	28 December 2017	Novo Nordisk
Version:	4.0	
Status:	Final	
Page:	47 of 124	

Patients should be informed to treat themselves at home according to the dosing schedule regardless of when visits 4, 5, 6, 7 and 8 are scheduled.

